## 1. Background

Lung cancer is the leading cause of cancer deaths worldwide, among which non-small cell lung cancer (NSCLC) accounts for more than 80% of newly diagnosed lung cancer cases. Even among early-stage (stage IB) patients, the 5-year survival rate is only 58%, suggesting that this group of patients is still at certain risk of recurrence, making combination of local control of the tumor and systemic therapy an important treatment modal for patients with surgically resectable NSCLC.

In studies of postoperative adjuvant therapy for NSCLC, a large meta-analysis made by the Non-small Cell Lung Cancer Collaborative Group in 1995 included 4767 patients. Results showed that the platinum-containing adjuvant chemotherapy regimen increased the 5-year overall survival (OS) by 5%, and although the results showed no statistically significant difference ( $P=0.08$ ), they initially established the place of the platinum-containing regimen in adjuvant chemotherapy for NSCLC. In the following decade, several randomized controlled clinical trials have compared various postoperative cisplatin-containing adjuvant chemotherapy regimens with surgery treatment alone. Several large randomized controlled clinical trials have been reported in the 21st century, some of which confirmed the overall survival benefit of adjuvant chemotherapy, but some still yielded negative results. In 2008, LACE made a meta-analysis of five large sample clinical trials after 1995, with 4584 patients and a median follow-up of 5.2 years. Results showed that the overall survival rate was benefited in the chemotherapy group ( $HR=0.89$ ,  $p=0.005$ ), with a 5-year survival rate increased by 5.4%, and the DFS in the chemotherapy group was also benefited ( $HR=0.84$ ,  $p<0.001$ ), with a 5-year DFS increased by 5.8%. Such meta-analysis also clarified the role of the 4-cycle platinum-containing regimen in increasing the 5-year survival rate in patients with stage II-IIIA NSCLC after complete resection. It is worth mentioning the CALGB9633 study, a randomized controlled study applying paclitaxel + carboplatin for adjuvant chemotherapy in all patients at stage IB, whose subgroup analysis confirmed that patients with tumor greater than 4 cm in diameter benefit from postoperative adjuvant chemotherapy.

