#### **7.1.3 Secondary efficacy**

Analysis of secondary efficacy variables includes:

- Disease Free Survival (DFS).
- Central nervous system (CNS)-related DFS.
- Overall survival (OS).
- Safety analysis: Safety and tolerability, quality of life. Adverse events and their most severe response grades will be summarized according to the criteria of NCI CTCAE version 4.0, and will also be summarized according to the severity and its relationship with the study drug. Descriptive summaries of laboratory test results focus on the outliers. Laboratory abnormalities will also be summarized by the most severe level in NCI CTCAE version 4.0.

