2.2 Secondary Objectives

To evaluate the efficacy of adjuvant icotinib, in terms of DFS, for patients with completely resected stage IB NSCLC, as compared with observation.

To evaluate the efficacy of adjuvant icotinib, in terms of central nervous system (CNS)-related DFS, for patients with completely resected stage IB NSCLC, as compared with observation.

To evaluate the efficacy of adjuvant icotinib, in terms of overall survival (OS), for patients with completely resected stage IB NSCLC, as compared with observation.

To assess the safety and tolerability of adjuvant 12-month icotinib for patients with completely resected stage IB NSCLC, as compared with observation.

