3.2 Randomization

Randomization will be performed by the study staff of the GASTO through a computer-generated sequence with a minimization method that balanced sex (male vs. female) and ECOG PS (0 vs. 1) for random assignment. Randomization will be performed just before the initiation of study administration. Eligible patients will be randomly assigned in a 1:1 ratio to either receive oral icotinib or undergo observation.

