4.1.2 Secondary Efficacy Endpoints

The secondary endpoints included DFS (time from random assignment to documented disease recurrence or death, whichever occurred first), central nervous system (CNS)-related DFS (time from randomization to CNS recurrence or death, whichever occurred first), overall survival (OS, time from random assignment to death from any cause).

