All analyses for efficacy are based on ITT population.

The Safety Analysis Set will include all subjects who received at least 1 dose of study drug and have a safety record after drug administration.

Descriptive statistics will be defined for continuous variables as number (n), median, mean, minimum and maximum, and as frequency and percentage for categorical variables.

The Kaplan-Meier method [2] will be used to estimate the point estimates of 3-year DFS for each group. The difference in 3-year DFS between groups will be compared by the Z test. The median DFS and OS will be estimated by the Kaplan-Meier method and the differences between median DFS and OS will be compared by the log-rank test.

Hazard ratios and their 95% confidence intervals for treatment effects are estimated using Cox proportional hazards models [3].

Unless otherwise specified, all statistical analyses will be performed using two-sided tests with a significance level of 0.05. All statistical analyses will be performed using SPSS and R.

11 Variables

Month=365/12 days.

Year=365 days.

Time since diagnosis to randomization = date of randomization – date of initial diagnosis) +1.

The duration of treatment was calculated as the (last dose date – first dose date) + 1.

Duration in study (days) = last day of known to be alive – date of randomization + 1

Follow-up time (days for DFS) = date of recurrence (patient who had recurrence) or date of last follow-up – date of randomization + 1.

Follow-up time (days for OS) = date of death (patient who died) or date of last follow-up – date of randomization + 1.

12 Missing data

No imputations will be made for missing data. Patients who does not have relapse or death will be censored at last follow-up.

13 References

3. Cox D. Regression models and life-tables. *J Royal Stat Soc Ser B*. 1972; 34: 187-220.

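### SAP 10 does not say that sex and ECOG PS, the two minimisation factors, enter the DFS, CNS-related DFS and OS analyses; a minor, cheaply mended gap confined to secondary endpoints

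*SAP*

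**What the plan says.** SAP 3.2 assigns patients 1:1 by "a minimization method that balanced sex (male vs. female) and ECOG PS (0 vs. 1) for random assignment".

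SAP 10 sets out the efficacy methods:
- Primary endpoint: "The difference in 3-year DFS between groups will be compared by the Z test", using Kaplan-Meier estimates.
- DFS and OS: "the differences between median DFS and OS will be compared by the log-rank test". No strata are given.
- Hazard ratios: "Hazard ratios and their 95% confidence intervals for treatment effects are estimated using Cox proportional hazards models". No covariates or strata are given.

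CNS-related DFS is an objective of its own in SAP 2.2 ("To evaluate the efficacy of adjuvant icotinib, in terms of central nervous system (CNS)-related DFS") and is defined in SAP 4.1.2 as "time from randomization to CNS recurrence or death, whichever occurred first". SAP 10 names no test for it, so only the general Cox sentence applies.

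Elsewhere in the SAP, sex is a baseline item (SAP 6) and an exploratory subgroup factor (SAP 9); ECOG PS is a baseline item only (SAP 6). Protocol 7.1.3 opens with "Analysis of secondary efficacy variables includes" and lists endpoints, but gives no method. On levels, SAP 5 ties the two-sided 10% to 3-year DFS, while SAP 10 sets two-sided 5% as the default.

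**The concern.** Minimisation makes the arms more alike on sex and ECOG PS than simple randomisation would. If those factors predict outcome, the treatment estimate varies less from trial to trial than an unadjusted analysis assumes. The unadjusted test is then conservative, and power that the allocation scheme has already paid for is not collected.

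The second matter is what is being estimated. A Cox hazard ratio adjusted for prognostic factors is conditional on them and differs a little from the unadjusted one. The SAP does not say which will be reported, so in an open-label trial the choice could be made after the data are seen.

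**Working it through.** **Inputs from the documents.** 128 patients, 1:1; 3-year DFS 60% against 77%, HR 0.5; 80% power at two-sided 10%; 2 years of accrual, 3 of follow-up; 5% dropout (all SAP 5). Default two-sided 5% (SAP 10). Stage IB 5-year survival 58% (Protocol 1).

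**Inputs assumed, because the documents give none.** Prognostic HRs of sex and ECOG PS; 40% of patients in each higher-risk level; independent factors; minimisation probability 0.9; exponential times.

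**1. The planned sample size.** Under HR 0.5, 3-year DFS is 0.60^0.5 = 77.5%. Freedman events: (1.645 + 0.842)² × (1.5/0.5)² = 6.18 × 9 = 55.6, so 56. Event probability over 5 years: control 1 − 0.6^(5/3) = 0.573; icotinib 1 − 0.6^(5/6) = 0.347; mean 0.460. Then 56/0.460 = about 121.8, and 121.8/0.95 = 128.2. The planned 128 is reproduced, counting every patient for 5 years, and with no covariate adjustment.

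**2. Closed-form anchor for the simulation.** With staggered entry and dropout, about 48 DFS events are expected. Log-rank power is Φ(√48/2 × ln 2 − z) with √48/2 × 0.693 = 2.401. At 10%: Φ(2.401 − 1.645) = 77.5%. At 5%: Φ(2.401 − 1.960) = 67.0%. The simulated log-rank values with no prognostic factors, 77.0% and 66.4%, agree.

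**3. DFS with and without the factors.** 40,000 simulated trials per scenario (Monte Carlo SE about 0.15 points for type I error, 0.21 for power), marginal 3-year DFS held at 60% and 77.5%. Adjusted Cox is the Wald test with arm, sex and ECOG PS.

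| Prognostic HR | Type I at 10%: log-rank / adj. Cox | Power at 10%: log-rank / adj. Cox | Gain | Power at 5%: log-rank / adj. Cox | Gain |
|---|---|---|---|---|---|
| Neither | 9.8 / 10.0 | 77.0 / 76.9 | −0.1 | 66.4 / 65.8 | −0.6 |
| 1.5 each | 9.6 / 10.3 | 76.7 / 77.6 | 0.9 | 65.8 / 66.7 | 0.9 |
| 2 for one | 9.4 / 10.4 | 76.7 / 78.1 | 1.4 | 65.4 / 67.0 | 1.6 |
| 2 each | 8.4 / 10.3 | 76.5 / 79.4 | 2.9 | 65.1 / 69.0 | 3.9 |

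Varying the minimisation probability (0.8 or 1.0), the prevalence of PS 1 (20% or 60%) and the correlation of the factors gives gains at 10% of 2.3 to 3.7 points (HR 2 each) and 0.7 to 1.2 (HR 1.5 each).

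**4. Independent repeats.** A second simulation held the treatment HR at 0.5 within factor levels, a slightly smaller marginal effect, with minimisation probability 0.8. At HR 2 each, power rises from 73.8 to 77.2% at the 10% level (3.4 points) and from 62.0 to 65.7% at 5% (3.7 points), with log-rank type I error 8.2% at nominal 10%. At HR 1.5 each the gain is 0.9 points at both levels (76.8 to 77.7%; 65.5 to 66.4%). A third, calibrated as in step 3 with 5,000 runs, gives 76.7 to 80.0% and 64.7 to 69.1% at HR 2 each, with log-rank type I error 7.8%.

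**5. Which hazard ratio.** At HR 2 each, the median estimate is 0.502 unadjusted and 0.479 adjusted (true conditional value 0.484). Reporting whichever Cox model looks better gives 10.3 to 11.1% error at nominal 10%.

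**6. OS and CNS-related DFS.** Taking 58% 5-year survival for control and an assumed OS HR of 0.5 gives about 34 deaths. Power at 10%, log-rank against adjusted Cox, is 63.6 / 63.1% (neither prognostic) and 64.4 / 66.3% (HR 2 each). CNS-related DFS counts every death, so it has at least as many events as OS; the documents give no CNS recurrence rate. If events are far fewer, adjustment hurts (neither prognostic, HR 0.5, nominal 10%): 42.5 / 40.8% at about 18 events, 32.8 / 28.5% at about 12, and 22.6 / 8.4% at about 6, where 25% of adjusted fits cannot be estimated.

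**The case against.** The case against acting has several parts.

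- The SAP is silent on Cox covariates; it does not rule them out. **This stands.** A reader might infer that the plan excludes the factors from every analysis. That is supported for the log-rank test, which is named without strata, but not for the Cox models or, therefore, for CNS-related DFS.
- The effect rests wholly on assumed prognostic strength. **This stands too**, and the range includes no gain. Stronger factors would cost more, but the documents give no basis for supposing them.
- Part of the gain reflects an adjusted Wald test running slightly above its level. On a normal approximation, setting it to exactly 10% cuts the gains at that level from 2.9 to about 2.5 points (HR 2 each) and from 0.9 to about 0.5 (HR 1.5 each). **This is fair, but approximate**, as the excess is about two Monte Carlo standard errors.
- Stratifying the planned log-rank test is a smaller change. It is, but in the second simulation at 10% it gains 2.4 points at HR 2 each and 0.1 at HR 1.5 each, and loses 1.4 (76.8 to 75.4%) if neither factor matters. It also leaves the Cox hazard ratio unspecified.

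A reader might also infer that ignoring the factors inflates false positives. The log-rank figures show the reverse: it stays at or below its level.

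**Conclusion.** The gap is real and minor. SAP 10 does not state that the minimisation factors are used for DFS, CNS-related DFS or OS. If both are clearly prognostic (assumed HR 2 each), the log-rank test is conservative, at about 8% for a nominal 10%, and about 4 points of DFS power are lost at the default 5% level (about 3 at 10%). At HR 1.5 each the loss is about 1 point; with neither prognostic there is none. The OS figures carry a further assumption, the OS hazard ratio, and no loss can be computed for CNS-related DFS.

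It would be tempting to read this as undermining the primary analysis or the sample size. The documents do not support that: 128 is reproduced without any adjustment, and the primary endpoint is a difference in 3-year proportions with its own named test. No stated figure is contradicted.

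**What to change.** In SAP 10, prespecify that for DFS, CNS-related DFS and OS the treatment hazard ratio, its 95% confidence interval and its test come from a Cox model with arm, sex and ECOG PS. State that this hazard ratio is conditional on those factors. Report the planned unadjusted log-rank test and the unadjusted hazard ratio alongside for each endpoint. Leave the Kaplan-Meier Z test for 3-year DFS as it is. Do not add an event-count rule that switches the main test: the documents offer no basis for a threshold.

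The cost is a few lines of text and code; both factors are known at randomisation, so no data or patients are added. If neither factor is prognostic, DFS loses 0.1 points of power at 10% and 0.6 at 5%, and OS loses 0.5 and 1.1. The adjusted Wald test runs at about 10.0 to 10.4% for a nominal 10%. The adjusted fit becomes unreliable with very few events, which is the reason for keeping the unadjusted result beside it.

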#### **3.6.1 Efficacy endpoints**

**Three-year Disease-Free Survival (DFS)** is defined as the proportion of patients who were disease free at 3 years.

**Disease-free survival (DFS)** is defined as the time between the date of randomization and the first confirmation of disease recurrence or death from any cause (whichever occurred first).

**Central nervous system (CNS)-related DFS** is defined as the time from randomization to CNS recurrence or death, whichever occurred first.

**Overall survival (OS)** is defined as the time between randomization and death from any cause. The 1-year overall survival is defined as the probability that the patient is alive for 1 year from the date of randomization. The 2-year overall survival is defined as the probability that the patient is alive for 2 years from the date of randomization. The 5-year overall survival is defined as the probability that the patient is alive for 5 years from the date of randomization.

The time that patients who are alive as of the date of analysis and are free of disease recurrence have

their last imaging evaluation is taken as the cutoff time.

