### 3.7.2 Visits

**Efficacy evaluation visits and subsequent visits (every 90 days  $\pm$ 7 days for the first 6 months and every 180 days  $\pm$ 7 days until 5 years)**

- Perform physical examinations (heart rate, blood pressure, respiratory rate, temperature, body weight and ECOG physical status scoring).
- Perform laboratory tests (hematology/blood biochemistry/urinary routine); perform ECG/pregnancy test.
- Collect biomarker samples (optional): take 10 ml of whole blood for molecular marker screening before treatment.
- Carry out tumor evaluation: it must include chest enhanced CT and upper abdomen enhanced CT. The follow-up period during treatment is every 3 months with an interval of +/- 7 days, covering the

chest and upper abdomen. All imaging tests can be replaced by PET/CT. Cranial MRI was scheduled every 12 months. Bone scan will be performed only when clinically indicated.

- Document adverse events and combined medications since the last visit.
- Make an appointment for a next visit.

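### The SAP's DFS-time formula omits the date of death, and its censoring date differs from the protocol's (wrong as written, minor)

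*SAP*

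**What the plan says.** **Event definition.** SAP 4.1.2 defines DFS as "time from random assignment to documented disease recurrence or death, whichever occurred first". Protocol 3.6.1 agrees and specifies death from any cause.

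**Derivation.** SAP section 11 gives "Follow-up time (days for DFS) = date of recurrence (patient who had recurrence) or date of last follow-up", less the randomization date, plus one day. The next line reads "Follow-up time (days for OS) = date of death (patient who died) or date of last follow-up", so the OS formula names the date of death and the DFS formula does not.

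**Censoring.** SAP section 12 says "Patients who does not have relapse or death will be censored at last follow-up". For patients alive and free of recurrence at the analysis, protocol 3.6.1 says that "their last imaging evaluation is taken as the cutoff time". The SAP does not define last follow-up, and nothing in either document reconciles the two rules.

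**Use.** SAP section 10 estimates 3-year DFS, the primary endpoint, by Kaplan-Meier in each arm and compares the arms by a Z test. This time variable is the input.

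**The concern.** A patient who dies without recurrence has a DFS event, but the formula offers only a recurrence date, which does not exist, or a last follow-up date. Read literally, the event is placed on some day other than the day of death. Whether that day is earlier or later depends on what last follow-up means.

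For a patient with neither event, the SAP allows disease-free time to run to the last contact, while the protocol stops it at the last scan. Time without imaging in which a recurrence could have gone unseen would then count as disease-free.

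Two programmers working from these documents could give the same patient different times in the primary analysis.

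**Working it through.** The documents give no figure for this point to reproduce. The text comparison settles whether there is an error; the arithmetic only illustrates its size.

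**Text comparison**

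| Patient | SAP 4.1.2, protocol 3.6.1 | SAP 11 | SAP 12 |
|---|---|---|---|
| Recurrence | event, recurrence date | recurrence date | not censored |
| Death without recurrence | event, date of death | last follow-up date | not censored |
| Neither | protocol: last imaging | last follow-up date | censored at last follow-up |

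The second row is a contradiction within the SAP. The third is a conflict between the SAP and the protocol.

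**Inputs from the documents.** Control 3-year DFS is 60% and the HR is 0.5 (SAP section 5). With exponential DFS, icotinib 3-year DFS is 0.6^0.5 = 77.5% (the SAP rounds to 77%). Allocation is 1:1 with 128 patients, so 64 per arm. A year is 365 days (SAP section 11), so 3 years is day 1095. Visits run every 90 days "for the first 6 months and every 180 days" (protocol 3.7.2); footnote G to the study flow chart has tumor evaluation every 6 months in follow-up.

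**Assumed, because the documents do not say.** Recurrence-free deaths are a share q = 5%, 10% or 20% of first DFS events. A share m of patients stops scans, uniformly over 3 years, but stays in contact to the data cut, with no event recorded after the last scan.

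**Misdated deaths** (full follow-up, S = DFS function, change in 3-year DFS in points):

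- Dated back to the last 180-day visit before death. Deaths between days 1095 and 1260 move to day 1080. Change = −q × [S(1095) − S(1260)]. Control: −q × (0.6000 − 0.5555) = −0.22, −0.44, −0.89. Icotinib: −q × (0.7746 − 0.7454) = −0.15, −0.29, −0.58.
- Dated forward to the next visit, with visits exactly every half year. Deaths between days 912.5 and 1095 move to the 3-year visit, whose time is 1096 after the plus one day. Change = +q × [S(912.5) − S(1095)]. Control: +q × (0.6533 − 0.6000) = +0.27, +0.53, +1.07. Icotinib: +q × (0.8083 − 0.7746) = +0.17, +0.34, +0.67.
- If last follow-up is taken as the date of death itself: 0.

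So the sign depends on an undefined term.

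**Late censoring.** With everyone in contact past 3 years, the Kaplan-Meier value is the share with no recorded event: (1 − m) × S(1095) + m × (mean of S at the last scan). The rise is m × [mean S − S(1095)].

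- Last scan at the moment of stopping: mean S = (1 − S(1095)) / (−ln S(1095)). Control: 0.4/0.5108 = 0.783. Icotinib: 0.2254/0.2554 = 0.883.
- Last scan at the preceding half-yearly visit: mean of S at 0, 0.5, 1, 1.5, 2 and 2.5 years. Control 0.817, icotinib 0.901.
- With m = 5%, control: 0.05 × (0.783 − 0.600) = 0.92 to 0.05 × (0.817 − 0.600) = 1.08 points. Icotinib: 0.05 × (0.8825 − 0.7746) = 0.54 to 0.05 × (0.9014 − 0.7746) = 0.63 points.
- Between-arm shift with equal m: 0.92 − 0.54 = 0.38 to 1.08 − 0.63 = 0.45 points at 5%. It scales with m: about 0.75 to 0.9 at 10% and 1.5 to 1.8 at 20%. If only controls stop scans, at 5%, it is 0.92 to 1.08.

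**Yardstick.** The standard error of the difference in 3-year DFS is √(0.6 × 0.4/64 + 0.775 × 0.225/64) = 0.080, or about 8 points.

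**The case against.** The strongest reply is that the formula is merely incomplete. SAP 4.1.2, protocol 3.6.1 and SAP section 12 all treat a recurrence-free death as an event, so a programmer who reads them will use the date of death. That stands as to intent and is why the point is minor. It does not make the derivation line correct: the line gives two alternatives, neither is the date of death, and the OS line beside it lists death and last follow-up as separate dates.

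On censoring, the reply is that the dates normally coincide. Tumor evaluation continues every 6 months after treatment stops for reasons other than recurrence (protocol synopsis, Study Procedure), and telephone survival follow-up is planned only after recurrence (protocol 3.7.3). That also stands for patients who keep to the schedule. What remains is the patient who stays in contact but misses scans, and the documents give no rate for that. The protocol sentence does not name its endpoint, but its recurrence-free condition and imaging date fit DFS.

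Three stronger readings are tempting:

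- A reader might infer that recurrence-free deaths would be censored, so that the endpoint itself has changed. With q from 5% to 20%, control 3-year DFS would then read 0.6^(1 − q) = 61.6% to 66.5%. SAP 4.1.2 and section 12 rule this out.
- A reader might take the 5% illustration as a ceiling of about half a point on the between-arm shift. It holds only for equal 5% scan-stopping and one mechanism at a time.
- A reader might count CNS-related DFS as a further error, since SAP section 11 has no line for it and "Cranial MRI was scheduled every 12 months" (protocol 3.7.2). That is missing detail, not a contradiction: SAP 4.1.2 defines it as "time from randomization to CNS recurrence or death, whichever occurred first".

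**Conclusion.** Wrong as written, minor. The two text conflicts are certain. Their numerical effect is not: it rests on an assumed share of recurrence-free deaths, an assumed rate of scan-stopping, and exponential DFS at the planned rates. Under those assumptions each mechanism alone, at 5% scan-stopping, moves an arm's 3-year DFS by roughly a point or less, which is small beside the standard error. No upper bound is claimed, because more frequent or unequal scan-stopping gives more. Nor do the documents support a claim of bias towards icotinib: equal scan-stopping raises the control estimate more and so narrows the difference. The reason to act is that a stated rule for the primary variable contradicts its own definition and is easily put right.

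**What to change.** In SAP sections 11 and 12 state: DFS time = (earlier of first documented recurrence and death from any cause) − date of randomization + 1; patients with neither are censored at their last imaging evaluation showing no recurrence, or at randomization if there is none. This matches protocol 3.6.1. Leave the OS formula as it is. It would be enough to note that the same event rule, the earlier of CNS recurrence and death, applies to CNS-related DFS.

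The cost is a wording change and one revised derivation. Recurrence and death dates are already recorded (protocol 3.7.3) and imaging is already collected (protocol section 9). The downside is slightly shorter DFS follow-up for patients whose last contact had no scan.
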